#### **6.4.** MISSING DATA

For the analyses of various weekly responses, the week with missing assessments for more than 3 days will be treated as "non-responder" for the week. If a subject drops out of the study or otherwise does not report efficacy data for a particular treatment-period week, the subject will not be considered a responder for that week.

For the analyses of various weekly average scores for IBS symptoms, the weekly average score will be set to "missing" if there are more than 3 days with missing assessments during a week, and the data will be considered as "missing" for the week. An observed-cases approach to missing data will be applied to the continuous type variables; this means that if the data is considered as "missing" for the week, the average of the non-missing data over the 12 weeks of the treatment period will be the subject's value for that week.

Subjects will be assumed to have not had bowel movement nor taken rescue medication if the corresponding daily question is not answered.

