5.1 Pre-treatment period

Screening and Pre-treatment Period (up to 17 days prior to the first dose of study drug):

During the Screening and Pre-treatment Period, patients will be provided an ID number and password-protected access to the REDCap website to record baseline parameters (such as weekly average worst abdominal pain score and weekly number of CSBMs). During this period, patients will also (i) complete a lactulose breath test including analysis of methane, hydrogen, hydrogen sulfide, and carbon dioxide; (ii) provide a stool sample for analysis of the microbiome; and (iii) provide a blood sample for analysis of cytokines and baseline tests. Patients will be eligible for randomization if they have a breath methane level of \geq 10 ppm on the lactulose breath test and fully respond to the PRO questionnaires in the REDCap system on at least 11 of 14 days of the Screening and Pretreatment Period.

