# 2.2. DETERMINATION OF SAMPLE SIZE

The sample size calculation is based on the following assumptions: the weekly CSBM change from baseline is 0.5 for the placebo group, and 1.5 for each active group, with common standard deviation of 1.5. Fifty subjects in each group will have 90% power for each SYN-010 group compared with the placebo by using the t-test with 2-sided alpha = 0.05.

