#### 3.2. SECONDARY EFFICACY ENDPOINTS

The secondary efficacy endpoints are defined as below:

- Proportion of overall responders during the 12-week Treatment Period (overall 12-week responders). An overall 12-week responder is defined as a subject with a weekly response in at least 50% of the weeks of treatment (6 of 12 weeks). A weekly response is defined as a decrease in the subject's weekly average score for worst abdominal pain in the past 24 hours of at least 30% compared to baseline and a stool frequency increase of 1 or more CSBMs per week compared with baseline.
- Proportion of overall stool frequency responders during the 12-week Treatment Period. An
  overall stool frequency responder is defined as a subject with a weekly stool frequency
  response in at least 50% of the weeks of treatment (6 of 12 weeks). A weekly stool
  frequency response is defined as a stool frequency increase of 1 or more CSBMs per week
  compared with baseline, with abdominal pain unchanged or improved compared with
  baseline.
- Proportion of overall abdominal pain intensity responders during the 12-week Treatment Period. An overall abdominal pain intensity responder is defined as a subject with a weekly abdominal pain intensity response in at least 50% of the weeks of treatment (6 of 12 weeks). A weekly abdominal pain intensity response is defined as a decrease in the subject's weekly average score for worst abdominal pain in the past 24 hours of at least 30% compared to baseline, with stool frequency unchanged or improved compared with baseline.
- Proportion of overall bloating responders during the 12-week Treatment Period. An overall bloating responder is defined as a patient with a weekly bloating response in at least 50% of the weeks of treatment (6 of 12 weeks). A weekly bloating response is defined as a weekly average bloating score of at least 30% improvement compared to baseline, with stool frequency unchanged or improved compared with baseline.
- Proportion of patients using rescue medication.

Additional secondary endpoints are changes from baseline. The change from baseline at Visit X is defined as Value at Visit X – Value at Baseline. The percent change from baseline is defined as (change from baseline)/baseline value. If the baseline value = 0 or missing, then the percent change from baseline will be missing.

• Change from baseline in weekly average score for worst abdominal pain at Weeks 1 through 12.

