#### 6.2. BASELINE AND STUDY DAY DEFINITIONS

Baseline definition will vary upon the data/variables for summaries/analyses.

Table 1: Baseline Definitions

Data/Variables	Baseline Definition
Laboratory, vital signs, and ECG	The last non-missing value prior to the first dose of the study drug
Breath CH 4 AUC measurement	AUC of breath CH 4 measurements collected during lactulose breath test performed at Screening after an overnight fast
Singe-point breath CH 4 measurement	A single-point breath CH 4 measurement collected at Randomization after an overnight fast
Weekly average score for worst abdominal pain in the past 24 hours	(Sum of daily pain scores) / (number of days with pain score assessment during the 7 days prior to the first dose of study drug)
Stool frequency of CSBMs per week/Weekly average number of CSBMs	7 x (sum of daily number of CSBMs) / (number of days with CSBM assessment

	during the 7 days prior to the first dose of study drug)
Stool frequency of SBMs per week/Weekly average number of SBMs	7 x (sum of daily number of SBMs) / (number of days with SBM assessment during the 7 days prior to the first dose of study drug.
Weekly average of bloating score	Sum of daily bloating scores / (number of days with bloating score assessments during 7 days prior to the first dose of study drug)
Weekly average of straining score	Sum of daily straining scores / (number of days with straining score assessments during 7 days prior to the first dose of study drug)
Adequate Relief	The last non-missing value prior to the first dose of the study drug
Weekly stool consistency score (BSFS)	Sum of (i $\times$ number of type i stools) / total number of stools during 7 days prior to the first dose of study drug, where stool consistency i = 1, 2,7
EQ-5D-5L score	The last non-missing value prior to the first dose of the study drug

Study day will be defined as follows:

- The first dose of study drug is designated as Day 1.
- For visit days after Day 1, study day = visit date Day 1 date + 1.
- For visit days prior to Day 1, study day = visit date Day 1 date. Thus, study days for screening visit are negative numbers. There is no "Day 0".

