The analysis will be conducted based on the following imputation method: If a subject drops out of the study or otherwise does not report efficacy data for a particular treatment-period week, the subject will not be considered a responder for that week. The weekly response will not be considered a responder if there are more than 3 days with missing assessments during a week.

Two sensitivity analyses for the overall responders will be conducted: (1) missing data for the responders will be imputed as "responders"; (2) the overall responders are defined based on the LOCF for missing values of the weekly average score for worst abdominal pain and/or weekly average number of CSBMs.

Additional secondary endpoints are change from baseline. The change from baseline at Visit X is defined as Value at Visit X - V alue at Baseline. The percent change from baseline is defined as (change from baseline)/baseline value. If the baseline value = 0 or missing, then the percent change from baseline will be missing.

- Change from baseline in weekly average score for worst abdominal pain at Weeks 1 through 12. Weekly average score for worst abdominal pain = (sum of daily worst abdominal pain scores) / (number of days with worst abdominal pain score assessment for the specific week).
- Percent change from baseline in weekly average score for worst abdominal pain at Weeks 1 through 12. Percent change from baseline in weekly average score for worst abdominal pain = (the weekly average score for worst abdominal pain for the specific week the weekly average score for worst abdominal pain at baseline) / (the weekly average score for worst abdominal pain at baseline).
- Change from baseline in weekly average number of CSBMs at Weeks 1 through 12. Weekly average number of CSBMs = 7 x (sum of daily number of CSBMs) / (number of days with CSBM assessment) for the specific week.

- Change from baseline in weekly average number of SBMs at Weeks 1 through 12. Weekly average number of SBMs = 7 x (sum of daily number of SBMs) / (number of days with SBM assessment) for the specific week.
- Change from baseline in weekly average bloating score at Weeks 1 through 12. Weekly average bloating score = (sum of daily bloating scores / number of days with bloating score assessment) for a specific week.

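### SAP 6.4 counts unanswered diary questions as none but does not reconcile this with its missing-week rule or the CSBM denominator, so one diary can give different primary values; its observed-cases rule is also, in fact, an imputation

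*SAP*

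**What the plan says.** SAP 6.4 contains three rules for incomplete diaries.

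- A weekly average score is set to missing when more than 3 days of that week lack an assessment.
- "An observed-cases approach to missing data will be applied to the continuous type variables". The SAP explains this as giving the missing week "the average of the non-missing data over the 12 weeks of the treatment period".
- "Subjects will be assumed to have not had bowel movement nor taken rescue medication if the corresponding daily question is not answered".

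Other sections bear on the same data.

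- SAP 8.2.1 sets weekly CSBMs at seven times the summed daily counts, divided by "number of days with CSBM assessment) for the specific week".
- SAP 6.2, Table 1, uses the same form for baseline, over the 7 days before the first dose: "7 x (sum of daily number of CSBMs) / (number of days with CSBM assessment".
- Protocol 5.1 admits patients who "fully respond to the PRO questionnaires in the REDCap system on at least 11 of 14 days".
- SAP 3.1 calls a movement spontaneous only if no rescue or other laxative was used that day or the day before.
- SAP 3.2 requires a "stool frequency increase of 1 or more CSBMs per week" for the weekly stool frequency response.
- SAP 8.1 bases the primary ANCOVA on observed values, with multiple imputation and LOCF as sensitivity analyses.

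**The concern.** The third rule in 6.4 turns a gap into a recorded zero. The denominator in 6.2 and 8.2.1 leaves a gap out. The more-than-3-days rule discards the week. Nothing gives these an order, says whether an unanswered day is an assessed day, or says whether a skipped item or a whole missing diary day is meant. It is also unclear whether the missing-week rule, which is worded for symptom scores, covers CSBM and SBM counts. If an unanswered day is an assessed zero, that rule can never apply to CSBMs.

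At stake are the baseline covariate, the weekly CSBM values, the CSBM part of the responder definitions and the primary endpoint. Conditional power on the primary endpoint also feeds the futility rule in Protocol 6.6. Two programmers could follow the SAP and deliver different primary results.

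The fill is a separate and smaller matter. It carries the name of one method and describes another.

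**Working it through.** **1. The plan's own figure.** SAP 2.2 assumes that "the weekly CSBM change from baseline is 0.5 for the placebo group, and 1.5 for each active group", with SD 1.5 and 50 per group. The planned difference is 1.5 − 0.5 = 1.0. At two-sided alpha 0.05, power is 91.5% (normal approximation) or 91.0% (noncentral t), in line with the stated 90%.

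**2. One diary, two values.**

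| Diary | Gaps left out | Gaps as assessed zeros |
|---|---|---|
| Treatment week, 2 CSBMs on 4 answered days | 7 × 2/4 = 3.5 | 7 × 2/7 = 2.0 |
| Treatment week, 2 CSBMs on 3 answered days | missing (4 days absent) | 7 × 2/7 = 2.0 |
| Baseline, 1 CSBM on 4 answered days | 7 × 1/4 = 1.75 | 7 × 1/7 = 1.0 |

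Against a baseline of 2.0, the first row is a change of +1.5 (criterion met) or 0 (not met). The third row can occur: 11 complete days of 14 leave 3 incomplete, and all 3 may fall in the 7-day baseline window.

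**3. Effect on the planned difference if gaps become zeros.** Let b be mean baseline CSBMs per week, and m the share of treatment days unanswered in an arm. The documents give neither, so both are assumed. With a complete baseline diary and gaps unrelated to outcome,

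difference = (b + 1.5)(1 − m_active) − (b + 0.5)(1 − m_placebo).

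- Equal shares: this reduces to 1.0 × (1 − m), which is 0.95, 0.90 or 0.80 at 5%, 10% or 20%.
- 20% active, 10% placebo: b = 0.5 gives 2.0 × 0.8 − 1.0 × 0.9 = 0.70; b = 2.0 gives 3.5 × 0.8 − 2.5 × 0.9 = 0.55.
- 10% active, 20% placebo: b = 0.5 gives 2.0 × 0.9 − 1.0 × 0.8 = 1.00; b = 2.0 gives 3.5 × 0.9 − 2.5 × 0.8 = 1.15.

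**4. The rescue half of the rule.** Suppose baseline is 2.0 and the bowel questions are answered on all 7 days. Two complete movements are clearly laxative-free. A third falls on a day when a laxative was taken but the laxative question was left blank. The rule gives 3 CSBMs, a change of +1.0 (met). The true answer gives 2, a change of 0 (not met). Treating the day as missing gives 7 × 2/6 = 2.33, a change of +0.33 (not met). Because the SBM definition looks back one day, one blank can affect movements on two days. This error raises CSBMs, whereas a blank bowel-movement item lowers them.

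**5. The fill.** If k weeks are observed with mean M, filling the other 12 − k with M gives [kM + (12 − k)M]/12 = M. For example, weeks 1, 1, 2, 2, 3, 3, 4, 4 average 20/8 = 2.50; after the fill, (20 + 4 × 2.50)/12 = 2.50. The 12-week mean is unchanged, but Week 12 becomes 2.50 instead of missing.

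This holds only if the average is taken over weekly values. A week with 7 CSBMs on 7 days and a week with 1 on 4 days average (7 + 1.75)/2 = 4.38 by week, but 7 × 8/11 = 5.09 over pooled days.

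The fill also makes by-week SEs smaller than that week's own data support. Assume weekly SD 2.0, correlation 0.6 between weeks and with baseline, 50 per arm, exits after Weeks 1 to 7 and dropout of 4/53 (Protocol 6.6). Simulated ANCOVA SEs at Week 12 are then about 0.32 filled and 0.33 observed, a gap of about 5% before rounding.

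**The case against.** The strongest reply is that the rule speaks of a daily question, and the diary in Protocol 13.3 is a set of separate questions. A skipped item on an otherwise completed day is the natural reading, and whole missing days then fall under the 3-day rule. That is probably the intent. But the SAP does not say so, and even then it leaves open whether such a day enters the denominator.

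Second, every unanswered share above is assumed. Entry requires 11 of 14 complete days, and Protocol 9.1 provides for continuing compliance review, so gaps may be few. Gaps at baseline precede randomization and do not systematically bias the treatment difference. All of this stands. It limits the likely size but does not settle the derivation.

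Third, the fill is at least stated, and replacing it is partly preference. That also stands, which is why it is the minor part here.

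A reader might infer three stronger claims:

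- *All weeks after withdrawal become zeros.* This strains the text. It would leave the 3-day rule with nothing to do for CSBMs.
- *The fill distorts the primary result.* Step 5 shows that it does not if the primary value is the mean of weekly values. The responder endpoints are also untouched, because missing weeks count there as non-response.
- *The trial loses substantial power.* Holding SD at 1.5, a difference of 0.90 gives about 84%. But zeros applied equally in both arms also shrink the spread of the counts, so that figure overstates the loss.

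**Conclusion.** The conflict in SAP 6.4 is real and reaches the primary endpoint. The documents do not determine a patient's weekly or baseline CSBM value when diary answers are missing. For a single week the choice can be worth 1.5 CSBMs, enough to reverse the response criterion. For the planned difference of 1.0, counting gaps as zeros gives 0.95 to 0.80 at equal unanswered shares of 5% to 20%. With 20% in one arm and 10% in the other it gives 0.55 to 1.15, for a baseline of 0.5 to 2.0 CSBMs per week. Shares and baseline are assumptions. The net direction is not fixed, because blank rescue answers act the opposite way and may also differ by arm.

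The own-mean fill is a mislabelled imputation of minor consequence. It brings other weeks' data into by-week ANCOVAs that carry nominal P-values outside the fixed sequence, and it shortens their SEs by about 5% under the stated assumptions. It should not be presented as a threat to the primary test.

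**What to change.** In SAP 6.4, with matching wording in 6.2 and 8.2.1:

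1. Apply the more-than-3-missing-days rule first, and state that it covers CSBMs and SBMs.
2. Treat a day with no diary entry as not assessed, and leave it out of the denominator for baseline and treatment weeks.
3. Limit the assumption of none, for bowel movements and for rescue use, to a blank item on a day with a diary entry. State whether that day counts in the denominator.
4. Add a sensitivity analysis that treats such days as missing.
5. Delete the fill, so that missing weeks stay missing in the by-week analyses. In 8.1, define the primary value as the mean of the patient's non-missing weekly values, and run multiple imputation and LOCF on the unfilled weekly data.

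The cost is a few sentences, modest programming and one extra sensitivity analysis. No new data are needed and the sample size does not change. There are two downsides. By-week SEs become slightly larger, and observed cases can be biased if outcome-related dropout differs between arms. Deleting the fill therefore makes the stated method and the analysis agree; it does not guarantee less bias. The rules should be settled before unblinded results could influence the choice.

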# 7. DEMOGRAPHIC AND BASELINE CHARACTERISTICS

#### 7.1. SUBJECT DISPOSITION AND WITHDRAWALS

The number of all randomized subjects and the number and percentage of subjects in each analysis population will be presented by treatment group. The number of subjects who completed the study and the number who discontinued prematurely and the reason for discontinuation will be presented by treatment group for randomized subjects.

For the screen failure subjects, reasons for screen failure will be summarized separately.

#### 7.2. DEMOGRAPHIC AND OTHER BASELINE CHARACTERISTICS

Demographics and baseline characteristics will be summarized by treatment group for the full analysis set.

Demographics and baseline characteristics include: age, gender, race, ethnicity, baseline breath methane values, height, weight, and body mass index (BMI).

- Height (in cm) = height (in inches) \* 2.54
- Weight (in kg) = weight (in lbs) \* 0.4536

#### 7.3. MEDICAL/SURGICAL HISTORY

Medical/surgical history collected at Screening will be coded using the Medical Dictionary for Regulatory Activities (MedDRA).

These data will be summarized by system organ class (SOC) and preferred term (PT) and treatment group for the full analysis set.

#### 7.4. MEDICATION

Medications will be coded with generic names using IBM Micromedex, which is a collection of drug databases.

## 7.4.1. Prior Medication

Prior medications will be defined as medications with a start date prior to the first dose of study drug. The stop date of the medication may be before or after the first dose of study drug or the medication may be ongoing. If a start date is completely missing, the medication will be considered a prior medication.

#### 7.4.2. Concomitant Medications

Concomitant medications will be defined as medications with a stop date on or after the first dose of study drug or any medication that is ongoing. The start date of the medication may be before or after the first dose of study drug. A medication with completely missing use dates or partially

missing use dates without evidence that the medication was stopped prior to the first dose of study drug will be considered a concomitant medication.

Concomitant medications will be summarized by ATC level 2 term, PT, and treatment group for the full analysis set.

# 7.5. PROTOCOL DEVIATIONS

Major protocol deviations will be summarized by treatment group for the full analysis set. The categorization (e.g., informed consent, inclusion/exclusion, missing assessment) and classification (major/minor) of protocol deviations will be performed prior to database lock.

# 8. EFFICACY ANALYSIS

Observed data at each time point and change from baseline to each post-baseline visit/time point will be summarized by treatment group. For categorical data, frequency counts and percentages will be presented over time by treatment group.

All efficacy analyses will be performed on the full analysis set, and efficacy analyses will be conducted according to the randomized treatment the subjects receive. Sensitivity analyses of the primary efficacy endpoint and selected secondary efficacy endpoints will be performed. In addition, an analysis of the primary efficacy endpoint and selected secondary efficacy endpoints will be performed for the per protocol population.

#### 8.1. PRIMARY EFFICACY ENDPOINT AND ANALYSIS

The primary endpoint is the change from baseline in the weekly average number of CSBMs during the 12-week treatment period.

The analysis for the primary endpoint will be performed using the analysis of covariance (ANCOVA) with treatment group and the baseline value as covariates based on the full analysis set. The primary analysis will be conducted using the observed values. To control the overall false positive rate at 0.05, the Hochberg testing procedure will be used. Specifically, let  $P_1$  and  $P_2$  be the P-values from the ANCOVA comparing the 42 and 21 mg dose group with the placebo, respectively, if  $Max(P_1,P_2) \leq 0.05$ , then the primary endpoint will achieve statistical significant for both doses. Otherwise, if  $Min(P_1,P_2) \leq 0.025$ , then the primary endpoint will achieve statistical significance for the dose that has smaller P-value. If  $Min(P_1,P_2) > 0.025$ , then the primary endpoint will not achieve statistical significance for either dose group. The nominal P-values and 95% confidence intervals (CI) will be provided from the ANCOVA model.

Two sensitivity analyses will be conducted by using the multiple imputation and last observation carried forward (LOCF) methods to impute the missing data for the primary endpoint. The same ANCOVA model will be used for the sensitivity analyses.

In addition, the analyses of the primary endpoint will be performed based on the PP population using the same statistical model.

# 8.2. SECONDARY AND EXPLORATORY EFFICACY ENDPOINTS AND ANALYSIS

# 8.2.1. Secondary Efficacy Endpoints

The secondary efficacy endpoints are listed below:

- The proportion of overall responders during the 12-week Treatment Period (overall 12-week responders).
- Proportion of overall stool frequency responders during the 12-week Treatment Period.
- Proportion of overall abdominal pain intensity responders during the 12-week Treatment Period.
- Proportion of overall bloating responders during the 12-week Treatment Period.

• Proportion of patients using rescue medication.

The comparisons of the proportions will be performed using the Chi-squared test for equal proportions based on the full analysis set. The Chi-squared test from SAS Proc Freq will be used for the comparison of the treatment differences (each SYN-010 dose group versus placebo). Nominal P-values and 95% Newcombe-Wilson CIs for treatment differences will be presented.

To control the overall false positive rate, a fixed sequence testing procedure will be used for the testing of the secondary endpoints listed above. Specifically, the secondary endpoints will be tested formally if statistical significance is achieved for the primary endpoint for both dose groups, otherwise, the secondary endpoints will not be tested formally. If statistical significance is achieved for the primary endpoint for both dose groups, then the secondary endpoints will be tested formally in the order of the list for the 42 mg dose. The first listed secondary endpoint will be tested at the 2-sided alpha = 0.05 level. If statistical significance is not achieved, then the testing procedure will stop. If statistical significance is achieved for the first listed secondary endpoint, then the following secondary endpoint will be tested at the 2-sided alpha = 0.05 level. The testing procedure will continue for the testing of the secondary endpoints until statistical significance is not achieved for a secondary endpoint for the 42 mg dose group. If statistical significance is achieved for all listed secondary endpoints of the 42 mg dose group, then the testing procedure will be repeated for the 21 mg dose group.

The analysis will be conducted based on the following imputation method: If a subject drops out of the study or otherwise does not report efficacy data for a particular treatment-period week, the subject will not be considered a responder for that week. The weekly response will not be considered a responder if there are more than 3 days with missing assessments during a week.

Two sensitivity analyses for the overall responders will be conducted: (1) missing data for the responders will be imputed as "responders"; (2) the overall responders are defined based on the LOCF for missing values of the weekly average score for worst abdominal pain and/or weekly average number of CSBMs.

Additional secondary endpoints are change from baseline. The change from baseline at Visit X is defined as Value at Visit X - V alue at Baseline. The percent change from baseline is defined as (change from baseline)/baseline value. If the baseline value = 0 or missing, then the percent change from baseline will be missing.

- Change from baseline in weekly average score for worst abdominal pain at Weeks 1 through 12. Weekly average score for worst abdominal pain = (sum of daily worst abdominal pain scores) / (number of days with worst abdominal pain score assessment for the specific week).
- Percent change from baseline in weekly average score for worst abdominal pain at Weeks 1 through 12. Percent change from baseline in weekly average score for worst abdominal pain = (the weekly average score for worst abdominal pain for the specific week the weekly average score for worst abdominal pain at baseline) / (the weekly average score for worst abdominal pain at baseline).
- Change from baseline in weekly average number of CSBMs at Weeks 1 through 12. Weekly average number of CSBMs = 7 x (sum of daily number of CSBMs) / (number of days with CSBM assessment) for the specific week.

- Change from baseline in weekly average number of SBMs at Weeks 1 through 12. Weekly average number of SBMs = 7 x (sum of daily number of SBMs) / (number of days with SBM assessment) for the specific week.
- Change from baseline in weekly average bloating score at Weeks 1 through 12. Weekly average bloating score = (sum of daily bloating scores / number of days with bloating score assessment) for a specific week.
- Change from baseline in weekly stool consistency score (BSFS) at Weeks 1 through 12. Weekly stool consistency score = sum of (i × number of type i stools in a week) / total number of stools in the specific week, where i = 1, 2,...7.
- Proportions of overall abdominal pain intensity responders with different cutoff points for the % improvement from baseline in weekly average score for worst abdominal pain, i.e., ≥ 10%, 20%, 40%, 50%, 60%, and 70%.
- Proportions of overall stool frequency responders with different cutoff points for the improvements from baseline in the weekly number of CSBMs  $\geq 2, 3, 4, 5$ , and 6.

Proportions of overall bloating responders with different cutoff points for the % improvement from baseline in weekly average bloating score, i.e.  $\geq$  10%, 20%, 40%, 50%, 60%, and 70%.

The same analysis of covariance (ANCOVA) model will be used for the analysis of the continuous secondary endpoints. The model will include treatment group and the corresponding baseline value as covariates. Nominal P-values and least squares treatment means and their differences will be presented, accompanied by 95% CIs for each time point. The comparisons of the proportions will be performed using the Chi-squared test for equal proportions.

All analyses will be based on the full analysis set.

